11.3 Period for recording adverse events

Data on serious adverse events, will be collected for the period the participant is taking part in the trial, i.e., from visit 1 to visit 6.

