Trial Design	Randomised, controlled, vaccine co-administration study with blinding
Trial Participants	Adults aged 50 and above with or without stable co-morbidities
Sample Size	
A total of 960 participants, consisting of two serology sub-cohorts (COVID-19, n=360; influenza, n=720); cell-mediated immunity (CMI) cohort CD4+ T cells (n=150) and exploratory immunology cohort (n=150). Participants will be randomised in a 1:1:2:2:2 ratio to one of five groups; 120 participants to groups 1 and 2, and 240 participants to groups 3-5. Only 120 participants in group 3 will progress to the second and third vaccination time points required to assess C19/RZV co-administration.
 
 • All five groups will receive two doses of RZV (except participants in group 3 who do not progress after the first vaccination timepoint and will not have any RZV doses as part of the trial) • At the first and second vaccination timepoints, participants will receive two injections (combinations of RZV, C19, aQIV or placebo)

	
 At the final vaccination visit participants will receive one injection (either second RZV, if in the vaccination season aQIV or C19 or placebo)
Planned trial period	
5 months per participant (following from the first study vaccination)
 
6 months for recruitment (following from first participant recruited)
 
28 months including trial set up and close down

	Objectives	Outcome Measures	Timepoint(s)
Co-primary immunogenicity outcomes	Immunogenicity, measured by S-binding total Ig, 1 month-after C19 vaccine given alone compared to co-administration with RZV (first or second dose)	Anti-spike total Ig	Days 0, 28, 56 & 84 Groups 1-3
	Immunogenicity, measured by haemagglutination inhibition assay (HAI), 1 month after aQIV for 3 of the strains included in the vaccine; HAI influenza A H3N2, HAI influenza A H1N1 and HAI influenza B	HAI	Days 0, 28, 56 & 84 Groups 3-5

	Victoria given alone compared to co- administration with RZV		
	Immunogenicity of 2 doses RZV vaccine, 1 month after the second dose, given alone, compared to co-administration with C19 or aQIV with either first or second dose of RZV	Anti-gE Ig	Days 0, 56, 84, & 140 Groups 1-5

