5.8.2 Visit 1: Recruitment and administration of trial vaccine

Once confirmed as potentially eligible volunteers will be asked to:

- Confirm they understand the contents of the ZosterFluCov trial PIL (this will be available via the pre-screening website)
- Discuss the trial with a member of the research team

Provide informed consent to participate, to the PI or an appropriately trained and delegated member of the study team, if willing to do so

If consent is given the participant will undergo the following:

- Medical history review
- History directed physical examination as required
- Eligibility confirmation by PI or medically qualified doctor
- Measurement of temperature, height and weight
- Complete Quality of Life questionnaire

Following consent and collection of baseline data, the participant will be randomised. The participant will then provide a blood sample for assessment of RZV, COVID-19 and influenza vaccine immunogenicity (immunogenicity and exploratory/CMI subsets*). Then, the trial vaccines will be administered. The participant will remain at the trial site for observation for at least 15 minutes following the vaccination, in case of immediate AEs.

In group 3 only 129 participants will progress to the second and third vaccination time points required to assess C19/RZV co-administration.

5.8.3 Between visit 1 and visit 2

In the period following the first visit and the second visit approximately 4 weeks later participants will be required to:

- Complete an electronic diary card for the first 7 days. This diary card will be used to capture:
 - AEs, including their timing and severity
- Report any hospitalisation as soon as is practically possible using the emergency 24-hour telephone number provided
- Report any other urgent medical concerns using the trial centre emergency procedures

- Report any unsolicited adverse events on the electronic diary card between day 8 and day 30 after vaccination
- Complete Quality of Life questionnaire 7 days after vaccination

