5.8.4 Visit 2: Safety review and blood sampling

At this visit, approximately 4 weeks after visit 1, participants will undergo the following:

- Safety review to assess for any serious adverse events
- Review and reconciliation of diary card data submitted
- Assessment for local and systemic adverse reactions and events and medical history since visit 1
- Provide blood sample for assessment of COVID-19, influenza vaccine immunogenicity
- Provide blood sample for exploratory immunology analysis*
- Participants in group 3 who will not be invited to continue the study will be informed and permission sought to follow up to resolution any clinically significant adverse events after the end of trial participation

5.8.5 Between visit 2 and visit 3

In the period between the second visit and the third visit approximately 4 weeks later participants will be required to:

- Report any hospitalisation as soon as is practically possible using the emergency 24-hour telephone number provided
- Report any other urgent medical concerns using the trial centre emergency procedures
- Report any unsolicited adverse events on the electronic diary card

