9.3 Samples remaining after all testing for this trial is completed

Participants will be informed that there may be leftover samples of their blood (after all testing for this trial is completed). Participants will be able to decide if they permit future use of any leftover samples.

With the participants' informed consent, any leftover serum or peripheral blood mononuclear cells will be kept for future analysis of COVID-19 and other coronavirus-related diseases or vaccine-related responses and other future research (exploratory immunology), including genotypic testing of genetic polymorphisms potentially relevant to vaccine immunogenicity.

If a participant elects not to permit this, all that participants' leftover samples will be discarded at the end of the trial.

Samples that are to be stored for future research will be transferred to a licenced Research Tissue Bank.

10. Definition of end of trial

The definition of the end of the trial is the date when all participants have completed visit 6, or are lost to follow-up, all samples have been analysed, the database has been locked and all data queries have been resolved.

The end of the trial for an individual patient is defined as completion of visit 6 or loss to follow-up.

11. Safety data collection and reporting

Participants will be asked to complete an electronic diary of solicited local (pain, redness, and swelling at injection site) and systemic (fatigue, fever GI symptoms (nausea, vomiting, diarrhoea and/or abdominal pain) headache, myalgia, shivering) AEs for 7 days after each vaccination.

Participants will be asked to record unsolicited AEs, up to 30 days after vaccination. Participants would be counselled with regard to expected side effects during the consent process and in the diary training. Leaflets about side effects would also be provided for participants.

Serious adverse events and adverse events of special interest (pIMDs) should be collected until the study end.

Safety monitoring

Safety monitoring would be continuous throughout the whole study and performed in real-time for the first 7 days after vaccination in the following ways:

- Participants would be required to complete electronic diary cards that would be reviewed in real time by trial physicians and the trial coordination team. All events will be reviewed, and reports of any grade 3 or above will trigger an alert to the relevant teams.

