12.5 Frequency and duration of follow up

Participants are followed up for 5 months from enrolment and randomisation. Pregnant women will be followed-up to delivery.

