A sample size of 240 per group will provide 80% power to test all part B hypotheses using a 2.5% one-sided significance level and allowing for 10% dropout.

Final sample size justification

A sample size of 960 (120 into groups 1 and 2, 240 into groups 3-5, after inflating to fit a 1:1:2:2:2 allocation ratio) will allow us to adequately assess all primary immunogenicity objectives.

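### Follow-up to visit 6 is stated for every participant although half of Group 3 finishes at visit 2, so Group 3's whole-study SAE/pIMD percentage would rest on about 60% of full planned follow-up

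*Protocol*

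**What the plan says.** Three protocol sections set follow-up without exception:

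- Section 11.3: SAE data "will be collected for the period the participant is taking part in the trial, i.e., from visit 1 to visit 6".
- Section 10: "The end of the trial for an individual patient is defined as completion of visit 6 or loss to follow-up".
- Section 12.5: "Participants are followed up for 5 months from enrolment and randomisation".

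The introduction to section 11 adds pIMDs and runs to the same end: "Serious adverse events and adverse events of special interest (pIMDs) should be collected until the study end".

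Other parts describe a planned early finish for half of one group. The synopsis (Table 1, sample size) states: "Only 120 participants in group 3 will progress to the second and third vaccination time points required to assess C19/RZV co-administration". It adds that those who do not progress receive no RZV dose in the trial. Figure 1 also shows half of Group 3 ending the study early. Section 5.8.4 handles this at visit 2: "Participants in group 3 who will not be invited to continue the study will be informed and permission sought to follow up" clinically significant adverse events to resolution. Section 12.7 pays this subset £90, against up to £270 for everyone else, at up to £45 per visit.

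The number who continue is given twice, differently. The synopsis says 120; section 5.8.2 says "In group 3 only 129 participants will progress".

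For reporting, section 13.4 makes the safety analysis descriptive, with the count and percentage of participants in each group for each safety outcome. The synopsis row for SAEs and pIMDs runs from the first vaccination to the end of the study and gives frequency and rate as the measure.

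**The concern.** The follow-up sections and the design sections cannot both be followed for the Group 3 participants who stop. Read literally, section 11.3 asks sites to record SAEs to visit 6 for people who have no visit after visit 2. Section 5.8.4 covers events already present at visit 2, with permission, but does not say whether new SAEs or pIMDs are to be sought afterwards.

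The reporting consequence follows from section 13.4. A percentage per group over the whole study has the same meaning across groups only if planned observation time is similar. In Group 3, half the denominator would be observed for about a month and half for about five. The two halves also differ in exposure: leavers receive aQIV and placebo only, while continuers go on to C19 with RZV at day 56 and RZV again at day 112. A reader comparing the five columns would see a Group 3 figure that tends to be low for reasons of design.

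**Working it through.** **1. Group sizes.** Section 13.1 gives "A sample size of 960 (120 into groups 1 and 2, 240 into groups 3-5", with a 1:1:2:2:2 allocation. Check: 2 × 120 + 3 × 240 = 960, which reproduces the stated total. With 120 continuers in Group 3, leavers number 240 − 120 = 120.

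**2. Last visit of the leavers.** From section 12.7, £90 / £45 = 2 visits and £270 / £45 = 6 visits. This agrees with section 5.8.4: visit 2 is their last.

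**3. Planned follow-up in Group 3.** Table 4 puts visit 2 at day 28 (window 26–32) and visit 6 at day 140 (window 140–146).

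Share = (continuers × day of visit 6 + leavers × day of visit 2) / (240 × day of visit 6)

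| Case | Person-days in Group 3 | Days per participant | Share of full follow-up |
|---|---|---|---|
| 120 continue, days 28 and 140 | 120 × 140 + 120 × 28 = 20,160 of 33,600 | 84 | 60.0% |
| 120 continue, days 26 and 146 | 120 × 146 + 120 × 26 = 20,640 of 35,040 | 86 | 58.9% |
| 120 continue, days 32 and 140 | 120 × 140 + 120 × 32 = 20,640 of 33,600 | 86 | 61.4% |
| 129 continue, days 28 and 140 | 129 × 140 + 111 × 28 = 21,168 of 33,600 | 88.2 | 63.0% |

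The second and third rows are the extremes across the visit windows.

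**4. Effect on a crude percentage.** The protocol gives no SAE or pIMD rate, so this step is illustrative. Assume the same risk in every group and a constant hazard. If the risk over 140 days is 2%, the risk by day 28 is 1 − 0.98^(28/140) = 0.40%. Group 3's expected percentage is (2.00% + 0.40%) / 2 = 1.20%, or 2.9 participants of 240 against 4.8 in a fully followed group of that size. For assumed risks from 1% to 5% the ratio stays at 0.60.

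**5. Dependence on event timing.** Let f be the fraction of the 140-day risk that falls by day 28. With 120 leavers, the ratio of Group 3's percentage to that of an equally risky, fully followed group is (120 + 120f) / 240 = (1 + f) / 2. It runs from 0.50 if all events come after day 28 (f = 0) to 1.00 if all come before (f = 1). The 60% share of follow-up is therefore firm arithmetic. The 40% shortfall in events holds only under a constant hazard.

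**The case against.** The strongest reply is that the protocol already treats visit 2 as the leavers' end of participation. Figure 1, section 5.8.4 and the payment rule all say so, and the first half of the quoted sentence in section 11.3 ties SAE recording to the time a person is taking part. On that reading the reference to visit 6 describes the full schedule, and only an exception is missing. This largely stands. A reader might infer that these participants have no rule at all; the documents do not support that. What remains is that the sentence's own gloss, with sections 10 and 12.5, says otherwise.

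A reader might also infer that, since section 10 allows only visit 6 or loss to follow-up, the leavers must count as lost, giving 120/960 = 12.5% against the less than 5% expected in section 12.6. The documents do not support that either. They describe a planned, trial-initiated completion, and nothing classes these people as lost.

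On analysis, the safety outcomes are descriptive, the SAE/pIMD entry names no comparator, the synopsis also lists a rate, and denominators may be settled in a statistical analysis plan that is not shown. These points limit the weight of the finding. They do not remove it, because the percentage per group is fixed in section 13.4 of the protocol itself.

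Finally, a constant hazard is doubtful when events may cluster after doses and other participants have further vaccination visits at days 56 and 112. That is accepted, and is why the working gives a range.

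**Conclusion.** The point holds as a contradiction in the protocol text with a limited consequence for reporting. Sections 10, 11.3 and 12.5 apply follow-up to visit 6 to everyone, while the synopsis, Figure 1 and sections 5.8.4 and 12.7 end participation at visit 2 for half of Group 3. Under the summary in section 13.4, Group 3's whole-study SAE/pIMD percentage would rest on about 60% of full planned follow-up, or 63% on the section 5.8.2 count, and would mix participants with and without RZV exposure in the trial.

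The likely direction is a lower figure in Group 3 without a true difference. Its size rests on an assumed event pattern and cannot be fixed from the protocol. No primary immunogenicity endpoint, success criterion or power figure is affected. The correction should still be made, because it is cheap and the per-group percentage would otherwise mislead.

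**What to change.** - In sections 10, 11.3 and 12.5, state that for non-continuing Group 3 participants both participation and SAE/pIMD recording end at visit 2, as a planned completion. The follow-up by permission in section 5.8.4 can remain as written.
- Report whole-study SAE, adverse event of special interest and pIMD outcomes per person-time, or show Group 3 leavers and continuers separately. Give the 140-day percentage only for participants scheduled to visit 6.
- Reconcile 120 with 129 for the number of Group 3 participants who continue.

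The cost is a few sentences of protocol text and one extra stratum in the safety table, with no change to sample size, visits or vaccines. The downside is a smaller Group 3 denominator for the 140-day percentage: 120 (or 129) instead of 240.

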11.4 Process for reporting serious adverse events

Centres should expedite reporting of SAEs to the coordinating centre and the Sponsor within 24 hours of becoming aware, using an SAE report form. If the event is classified as a SUSAR, the Sponsor will report the SUSAR to the MHRA and copy all reports to the coordinating centre; coordinating centre will report the SUSAR to the REC. These reports will be sent within 8 days for fatal or life-threatening events and 15 days for all other SUSARs.

11.5 Expected adverse events associated with trial interventions

Expected events are those listed in the Reference Safety Information (RSI), which for this trial is the summary of product characteristics (SmPC) for the vaccines (see Appendix). The RSI for each IMP is:

- RZV: Section 4.8 of the SmPC, dated 07/06/2022
- C19 vaccine: Section 4.8 of the SmPC, dated 05/2023
- aQIV: Section 4.8 of the SmPC, dated 06/2023

All other events that are not consistent in nature or severity with the SmPC should be considered unexpected. Fatal events will always be considered unexpected.

11.6 Expected adverse events associated with trial procedures

Localised bruising and discomfort can occur at the site of venepuncture. Infrequently fainting may occur. These will be documented as adverse events if they occur.

11.7 Events that will not be reported as serious adverse events (SAEs)

The following events will not be reported as SAEs:

- hospitalisation for a pre-existing condition, including planned elective procedures
- attendances at an emergency department unless they meet the SAE definition as described in Section 11.2.

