5.4 Trial population

Healthy adults aged 50 and over or those with established medical co-morbidities with stable symptoms on the day of randomisation and without prior history of shingles vaccination in the last 5 years. Prespecified maximum recruitment limits will be set for the following age groups; 69 and under and 70 and over to ensure that we have adequate representation of older adults for whom HZV is currently recommended. Recruitment of those from the global majority (Black, Asian and non-Caucasian groups) is particularly encouraged. Both men and women will be encouraged to participate.

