11.2 Definitions

Adverse event (AE) is any undesirable event in a subject receiving treatment according to the protocol, including occurrences which are not necessarily caused by or related to administration of the research procedures.

Adverse reaction (AR) is any undesirable experience that has happened to a subject while taking a drug that is suspected to be caused by the drug or drugs.

Serious adverse event (SAE) is any event which results in death, is life threatening, requires hospitalisation or prolongs hospitalisation, results in persistent or significant disability or incapacity, results in abnormal pregnancy outcomes or a congenital anomaly/birth defect in the offspring of a study participant, or any other event which may jeopardise the participant or require intervention to prevent one of the other outcomes listed above

Suspected serious adverse reaction (SSAR) is any serious adverse event that is suspected to be related to the drug or drugs being taken.

Suspected unexpected serious adverse reaction (SUSAR) is an untoward medical occurrence suspected to be related to the drug or drugs being taken that is not consistent with the applicable product information and is serious.

All AEs must be reviewed, and causality must be assessed by the PI or delegated individual not involved in the administration of the trial vaccines (to maintain blinding).

Severity grading for adverse events

The severity of adverse events will be assessed according to scales based on FDA toxicity grading scales for healthy adult volunteers enrolled in preventive vaccine clinical trials, listed in Table 6 and Table 7 below.

Table 6 Severity grading for local adverse events

Adverse Event	Grade	Intensity
Pain at injection site	0	No pain
	1	Pain that is easily tolerated
	2	Pain that interferes with daily activity
	3	Pain that prevents daily activity
	4	A&E visit or hospitalization
Redness at injection site*	0	<2.5 cm
	1	2.5- 5 cm
	2	5.1 - 10 cm
	3	>10 cm
	4	Necrosis or exfoliative dermatitis
Swelling at injection site	0	<2.5cm
	1	2.5 – 5 cm and does not interfere with activity
	2	5.1 - 10 cm or interferes with activity
	3	>10 cm or prevents daily activity
	4	Necrosis

Table 7 Severity grading for systemic adverse events

[figure not shown]
GRADE 0	None
GRADE 1	Mild: Transient or mild discomfort (< 48 hours); No interference with activity; No medical intervention/therapy required

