GRADE 2	Moderate: Mild to moderate limitation in activity – some assistance may be needed; no or minimal medical intervention/therapy required
GRADE 3	Severe: Marked limitation in activity, some assistance usually required; medical intervention/therapy required.

GRADE 4	Potentially Life-threatening: Requires assessment in A&E or hospitalisation
----------------	---

If an event meets any of the 'serious' criteria listed below it is classified as an SAE:

- a) Results in death
- b) Life threatening
- c) Requires hospitalisation (unless hospitalisation is pre-planned)
- d) Prolongation of existing hospitalisation
- e) Results in persistent or significant disability or incapacity
- f) Abnormal pregnancy outcomes, Congenital anomaly / birth defect
- g) Any other event which may jeopardise the participant or require intervention to prevent one of the other outcomes listed above

Figure 2 SAE* reporting process

**This will include pIMDs and AESIs that meet the definition of SAE*

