11.8 Adverse events of special interest

The following adverse events are considered adverse events of special interest (Table 8) and potential immune-mediated disorders (Table 9).

Table 8 Adverse events of special interest

Immunologic	Anaphylaxis	
Neurological	Isolated anosmia/ageusia*	Meningoencephalitis
	Guillain-Barre Syndrome	Peripheral facial nerve palsy
	Acute disseminated	Generalised convulsion
	encephalomyelitis (ADEM)	Myelitis
	Aseptic meningitis	

Haematological	Thrombosis** Stroke Thrombocytopenia (G3 or above) Eosinophilia	Coagulation disorder (includes coagulopathy, thrombosis, thromboembolism, internal/external bleed and stroke)
Cardiac	Acute cardiovascular injury (includes myocarditis, pericarditis, arrhythmias, heart failure, infarction)	
Dermatological	Chilblain-like lesions Single organ cutaneous vasculitis	Erythema multiforme Alopecia
Gastrointestinal	Acute liver injury	Appendicitis
Respiratory	ARDS	
Renal	Acute kidney injury	

**In the absence of COVID-19*

*** Excluding superficial thrombophlebitis (including line-associated)*

Table 9 List of potential immune-mediated diseases (pIMDs)

Medical Concept	Additional Notes
Blood disorders and coagulopathies	
Antiphospholipid syndrome	
Autoimmune aplastic anemia	
Autoimmune hemolytic anemia	
 Includes warm antibody hemolytic anemia and cold antibody hemolytic anemia

Autoimmune lymphoproliferative syndrome (ALPS)	
Autoimmune neutropenia	
Autoimmune pancytopenia	
Autoimmune thrombocytopenia	
 Frequently used related terms include: “autoimmune thrombocytopenic purpura”, “idiopathic thrombocytopenic purpura (ITP)”, “idiopathic immune thrombocytopenia”, “primary immune thrombocytopenia”.
Evans syndrome	
Pernicious anemia	
Thrombosis with thrombocytopenia syndrome (TTS)	
Thrombotic thrombocytopenic purpura	
 Also known as “Moschowitz-syndrome” or “microangiopathic hemolytic anemia”
Cardio-pulmonary inflammatory disorders	
Idiopathic Myocarditis/Pericarditis	
Including but not limited to:
 
 Autoimmune / Immune-mediated myocarditis Autoimmune / Immune-mediated pericarditis Giant cell myocarditis
Idiopathic pulmonary fibrosis	Including but not limited to:

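### Sections 11.2 and 11.7 conflict on whether an unplanned admission for a pre-existing condition is reported as an SAE

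*Protocol*

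**What the plan says.** Protocol section 11.2 gives two statements of what is serious. The running definition includes any event that "requires hospitalisation or prolongs hospitalisation", with no exception. The itemised list opens with "If an event meets any of the 'serious' criteria listed below it is classified as an SAE", and criterion c) reads "Requires hospitalisation (unless hospitalisation is pre-planned". Being pre-planned is the only exception to hospitalisation as a serious criterion, and neither statement mentions pre-existing disease.

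Section 11.7 opens with "The following events will not be reported as SAEs" and lists two items. The first is "hospitalisation for a pre-existing condition, including planned elective procedures". The second is "attendances at an emergency department unless they meet the SAE definition as described in Section 11.2".

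Section 5.4 admits healthy adults aged 50 and over, or "those with established medical co-morbidities with stable symptoms on the day of randomisation". Section 4.2 lists SAEs throughout the study as a secondary safety outcome. Section 11.4 requires sites to send SAEs to the coordinating centre and the sponsor within 24 hours, and the handling of SUSARs follows from that report. Section 14.3 makes a SUSAR a trigger for a safety review with a possible pause.

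**The concern.** The exemption in 11.7 is wider than the one in 11.2. A participant with stable heart disease, lung disease or diabetes at randomisation may be admitted as an emergency after a trial vaccination because that condition has worsened. Section 11.2 calls this an SAE, while 11.7 tells the site not to report it as one.

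The classification has consequences. Only an SAE carries the 24-hour report and enters the route to SUSAR assessment, and only SAEs count towards the SAE outcome. Section 12.2 plans about 15 sites. If some apply 11.2 and others 11.7, the SAE count will partly reflect which section each site followed. Randomisation is stratified by centre, which should limit imbalance between groups from this source. It does not restore the missing events, and it does not make the reported rates interpretable.

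**Working it through.** The protocol states no figure to reproduce, so the check compares the two sections case by case.

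1. **Admission planned in advance for a known condition.** Under 11.2 c) the hospitalisation does not make it serious. Under 11.7 it is not reported. The sections agree.
2. **Unplanned admission for a new condition.** It is serious under 11.2 c), and 11.7 does not mention it. The sections agree that it is an SAE.
3. **Emergency department attendance.** Section 11.7 sends the decision back to 11.2. The sections agree.
4. **Unplanned admission for a known condition.** Under 11.2 c) it is hospitalisation and was not pre-planned, so it is an SAE. Under 11.7 it is hospitalisation for a pre-existing condition, so it is not reported as an SAE. The sections conflict.

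Case 4 depends on the word *including* in the first 11.7 bullet, which makes planned procedures part of a larger exempt class. The second bullet carries an explicit return to the 11.2 definition and the first does not. No other section limits the exemption to planned admissions.

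The next question is what else would record a case 4 event:

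- **Hospitalisation reports.** Sections 5.8.3 to 5.8.11 ask participants to report any hospitalisation, so the site should learn of it.
- **Diary.** Unsolicited AEs are recorded to day 30 after each vaccination (5.8.3, 5.8.7, 5.8.11), and also between visits 2 and 3 and between visits 4 and 5 (5.8.5, 5.8.9). Thirty days after visit 5 is 112 + 30 = day 142, close to visit 6 at day 140 to 146. Diary collection therefore covers nearly all of follow-up.
- **AESIs and pIMDs.** Listed conditions are collected to study end (section 11). Table 8 includes "Acute cardiovascular injury (includes myocarditis, pericarditis, arrhythmias, heart failure, infarction". The note to Figure 2 brings these events into the SAE process if they meet the SAE definition.

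Collection is therefore broad, but the analysed unsolicited-AE outcome in section 4.2 stops 30 days after vaccination. On nominal visit days, for participants who complete all visits, the time outside that window is (56 − 30) + (112 − 86) = 26 + 26 = 52 of 140 days. In those 52 days, an admission for a worsened condition that is not on the AESI or pIMD lists, and that is withheld under 11.7, would be on the diary but in neither the SAE outcome nor the 30-day AE outcome.

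**The case against.** A reader might infer that these deteriorations are not counted at all, and that the DMSC could not see an excess with co-administration. The documents do not support that. Besides the capture routes above, section 11.2 requires review and causality assessment of all AEs. Diary reports of grade 3 or above in the first 7 days raise an alert (section 11), and Table 7 grades systemic events needing A&E assessment or hospitalisation as grade 4. The TMG reviews adverse events (14.2.2), and the DMSC receives safety reports (14.3). For listed conditions such as heart failure or arrhythmia, the note to Figure 2 points towards SAE reporting, so a site faces two conflicting instructions and not a clear rule to stay silent. The 11.7 bullet concerns hospitalisation only. It does not name death, life-threatening events or disability as exempt. Section 5.4.2 excludes unstable conditions at enrolment. Safety outcomes are descriptive (13.4), so no success criterion is affected.

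All of this stands and limits the consequence. It does not remove the conflict. An admission recorded as an ordinary AE does not get the 24-hour report or the route to SUSAR assessment. The Figure 2 note relies on the SAE definition, which returns the site to the disagreement between 11.2 and 11.7.

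**Conclusion.** The contradiction is real and confined to unplanned hospitalisation for a pre-existing condition. Its effect is misclassification: such events may be held as non-serious AEs at some sites and reported as SAEs at others, with loss of expedited reporting, SUSAR assessment and a place in the SAE outcome where 11.7 is followed. This rests on reading *including* in its ordinary sense. A site that takes the bullet to mean planned admissions only would act consistently with 11.2, and that possibility is itself the source of variation between sites.

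The number of events cannot be stated. A reader might apply an assumed admission rate to the participants planned to continue to visit 6 (120 + 120 + 120 + 240 + 240 = 840), but the documents give neither an admission rate nor the share due to known conditions. A reader might also suppose that worsening of existing disease is the commonest serious event in this population, and the documents do not say so. The non-inferiority analyses are unaffected. The point deserves correction because it governs how serious events are reported and the remedy costs almost nothing.

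**What to change.** Reconcile 11.7 with 11.2 c). Put the word *pre-planned* at the start of the first 11.7 bullet, so that it covers only pre-planned hospitalisation for a pre-existing condition, with elective procedures as the example. Add one sentence saying that unplanned hospitalisation for a pre-existing condition is reported as an SAE under 11.2. Conditions that 11.2 c) does not contain, such as planned before consent or not worsened since vaccination, should not be added to 11.7 alone, because they would create a new mismatch.

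The protocol does not show the status of the trial. If admissions have already been recorded when the change is made, check them against 11.2 and report any that were left out.

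The cost is one sentence in the protocol, the same wording in any SAE guidance to sites, and possibly a few more SAE forms. No visits, samples or assessments are added.
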